9.2.2 Serious Adverse Event Reporting

An adverse event or suspected adverse reaction is considered “serious” if, in the view of either the investigator or the sponsor, it results in any of the following outcomes:

- Death
- A life-threatening adverse drug experience – any adverse experience that places the patient, in the view of the initial reporter, at immediate risk of death from the adverse experience as it occurred. It does not include an adverse experience that, had it occurred in a more severe form, might have caused death.
- Inpatient hospitalization or prolongation of existing hospitalization
- A persistent or significant incapacity or substantial disruption of the ability to conduct normal life functions.
- A congenital anomaly/birth defect.

Important medical events that may not result in death, be life-threatening, or require hospitalization may be considered a serious adverse drug experience when, based upon appropriate medical judgment, they may jeopardize the patient or subject and may require medical or surgical intervention to prevent one of the outcomes listed in this definition. Examples of such medical events include allergic bronchospasm requiring intensive treatment in an emergency room or at home, blood dyscrasias or convulsions that do not result in inpatient hospitalization, or the development of drug dependency or drug abuse (21 CFR 312.32).

- Important medical events as defined above, may also be considered serious adverse events. Any important medical event can and should be reported as an SAE if deemed appropriate by the Principal Investigator or the IND Sponsor, IND Office.
- All events occurring during the conduct of a protocol and meeting the definition of a SAE must be reported to the IRB in accordance with the timeframes and procedures outlined in “The University of Texas M. D. Anderson Cancer Center Institutional Review Board Policy for Investigators on Reporting Serious Unanticipated Adverse Events for Drugs and Devices”. Unless stated otherwise in the protocol, all SAEs, expected or unexpected, must be reported to the IND Office, regardless of attribution (within 5 working days of knowledge of the event).
- **All life-threatening or fatal events**, that are unexpected, and related to the study drug, must have a written report submitted within **24 hours** (next working day) of knowledge of the event to the Safety Project Manager in the IND Office.
- Unless otherwise noted, the electronic SAE application (eSAE) will be utilized for safety reporting to the IND Office and MDACC IRB.
- Serious adverse events will be captured from the time of the first protocol-specific intervention, until 30 days after the last dose of drug, unless the participant withdraws consent. Serious adverse events must be followed until clinical recovery is complete and laboratory tests have returned to baseline, progression of the event has stabilized, or there has been acceptable resolution of the event.
- Additionally, any serious adverse events that occur after the 30 day time period that are related to the study treatment must be reported to the IND Office. This may include the development of a secondary malignancy.

Reporting to FDA:

- Serious adverse events will be forwarded to FDA by the IND Sponsor (Safety Project Manager IND Office) according to 21 CFR 312.32.

It is the responsibility of the PI and the research team to ensure serious adverse events are reported according to the Code of Federal Regulations, Good Clinical Practices, the protocol guidelines, the sponsor's guidelines, and Institutional Review Board policy.

9.2.3 Communication between Investigator and Jazz Pharmaceuticals

The Investigator must send all SAEs (initial and follow up) that require collection and reporting per protocol, and which occur in a patient who received CPX-351, to Jazz Pharmaceuticals within 1 business day of their awareness of the SAE via email to [contact]. In addition, all other adverse events must be reported to Jazz in summary of line-item form upon Jazz's request.

Follow-up information is sent either via a new Serious Adverse Event Form (stating that this is a follow-up), or via the original one form (with the new information highlighted and a new date provided). The follow-up should describe whether the event has resolved

or continues, if and how it was treated, whether the patient continued or discontinued study participation.

The telephone and fax numbers of the local Clinical Research contact person and the contact person in the local department of Clinical Safety, specific to the site, must be listed in the investigator folder provided for each individual site and provided to the manufacturer at the start of the trial. Questions referring to a specific serious adverse event occurring in a study patient should be directed to the local Clinical Research contact person specified in the investigator folder provided for the site.

9.3 Cardiac Toxicity Monitoring

As anthracyclines are known to have an adverse effect on cardiac function, each patient's cardiac function will be monitored through the Treatment and Follow-up Phases. Any left ventricular ejection fraction below 50% will be recorded as adverse events. If the left ventricular ejection fraction is reduced >10% to below 50% from the baseline assessment at the last Treatment Phase measurement, left ventricular ejection fraction will continue to be monitored every 3 months until a return to baseline or 1 year, whichever comes first.

9.4 Laboratory Data

Laboratory data obtained according to the schedule of assessments will be recorded on the CRF or other data collection instrument. Only laboratory data requested by the protocol need be recorded unless specific findings result in a clinical event such as an adverse event or documentation of peripheral blood count recovery. These results will be collected.

9.4.1 Copper Assessment

Patients will have serum copper assessed routinely and the percentage of patients with persistent (>1 year) copper elevations will be reported. Also, patients with persistently elevated serum copper will be evaluated for clinical abnormalities associated with copper toxicity (e.g. unexplained increase in liver function tests). Serum copper elevations are laboratory values and are not reported as adverse events unless associated clinical signs and symptoms of copper toxicity.

MDACC will draw the serum copper, send it out for processing and will report the results in clinic station in approximately 4 days.

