In this trial, serum copper levels will be monitored and elevated levels are assumed to be due to copper gluconate encapsulated within the CPX-351 liposome rather than free circulating copper. Clinical observation from a single patient treated with the identical copper-containing liposome encapsulating a different chemotherapy doublet (CPX-1, floxuridine and irinotecan) demonstrated sustained elevations of copper in a patient during a period of biliary obstruction, with return to baseline levels after stenting relieved the obstruction. This anecdote suggests that copper elimination after CPX-351 is likely via biliary excretion and elimination in the feces. Preclinical studies completed by Celator (acquired by Jazz Pharmaceuticals) demonstrated that virtually all of the copper administered in the form of CPX-351 is excreted via the feces within approximately 2 weeks of administration. It is expected that eligible patients with unobstructed biliary systems should be able to eliminate the copper administered within a few weeks. Serum copper levels will be monitored until they return to baseline levels ($\pm 20\%$) and patients will be monitored for hepatic dysfunction, a common manifestation of copper-related toxicity.

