4.6 Consolidation Therapy

Only patients with documented response (CR or CRi) are eligible for consolidation. Consolidation with stem cell transplant (HSCT) is permitted either in place of chemotherapy consolidation or after chemotherapy consolidation. Prior to beginning every other chemotherapy consolidation after the cumulative DNR dose exceeds 300 mg/m², or prior to every course of treatment after the cumulative DNR dose exceeds 500 mg/m², patient LVEF must be documented to be $\geq 50\%$ and patient PS must be 0-2.

Patients in CR with full recovery of peripheral blood counts within 56 days may be consolidated starting within one week of documentation of response. Patients with CRi may start consolidation no earlier than 42 days after the start of the last induction course

and only if ANC is $>500/\mu\text{L}$ and Platelets are $>50,000/\mu\text{L}$. Consolidation courses consist of 2 doses administered at 65 units/ m^2 on days 1 and 3.

A maximum of 4 courses of consolidation will be administered. It is understood that variations in timing of second induction and consolidations may be necessary and will be decided on a case by case basis by the PI. The rationale for variations in schedule will be documented by the PI. If consolidation is well tolerated and hematopoietic recovery is not delayed beyond 56 days, additional courses of consolidation may be offered immediately at time of recovery. In cases of poor patient tolerance or delayed hematopoietic recovery, the principal investigator will document his decision to either continue or terminate consolidation treatment.

Consolidation dosing:

First Consolidation	
Induction Outcome	Consolidation Dose
CR after induction ≤ 56 days	May start within one week of documentation of CR
CR after >56 days	Delay start of consolidation until day 70
CRi with at least ANC to $\geq 500/\mu\text{L}$ and platelets to $\geq 50,000/\mu\text{L}$	Starts after day 42.
CRi with ANC $<500/\mu\text{L}$ or platelets $<50,000/\mu\text{L}$	No consolidation to be given
Second and Subsequent Consolidations	
Previous Consolidation Outcome	Consolidation Dose
Count recovery to pre-consolidation baseline by Day 56	Same as first consolidation
Partial count recovery ANC ($\geq 500/\mu\text{L}$ and platelets to $\geq 50,000/\mu\text{L}$ by Day 56)	Delay second induction until day 70
Failure to recover (ANC $<500/\mu\text{L}$ or platelets to $<50,000/\mu\text{L}$) by Day 56	No consolidation to be given

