6.4 Evaluation during Long-term Follow-up

The following evaluations are completed during the follow-up phase (i.e., after completion of all therapy to continue for one year except for survival and relapse status which will continue until death and relapse, respectively):

Procedure	Evaluation	Timing
Patient status report	Survival status	Until death
	Relapse status New anti-leukemic therapies	Monthly until relapse or the initiation of new therapy
Hematology	Hemoglobin Hematocrit Red Blood Count White Blood Count Platelets Differential Count (may be omitted if WBC $\leq 0.5 \times 10^9/L$)	Every 2-3 months for one year until relapse or the initiation of new therapy, then as clinically indicated.
Bone Marrow Aspiration and/or Biopsy	Morphology	Every 3-4 months. For patients in CR, consider performing if peripheral blood counts fall below 1000/ μL for ANC or 100,000/ μL for platelets for >1 month with no obvious explanation for the drop or at any time there is suspicion of relapse; for patients in CRI perform if counts fall significantly below peak recovery. If the peripheral blood counts in a patient with a CRI recover to CR levels ($\geq 1000/\mu L$ for ANC or $\geq 100,000/\mu L$ for platelets), consider performing a bone marrow evaluation to confirm full CR. Following the first year of follow up, aspirations will be done as clinically indicated; record relapse information, including any bone marrow evaluations. Not required following the initiation of new therapy and or relapse.
Diagnostic Imaging	Echocardiography or MUGA	Perform every 3-4 months if last Treatment Phase LVEF was reduced >10% from baseline and is less than 50%. Continue assessments until LVEF returns to baseline or until 1 year from start of therapy.
Biochemistry	BUN Creatinine Bilirubin AST or ALT	Every 2-3 months for one year until relapse or the initiation of new therapy, then as clinically indicated.
Copper levels	Serum Copper	Perform monthly only if elevated copper (>20% above ULN) present at EOT. Perform every 1 month until abnormality returns to within 20% of ULN, or until 1 year, or the initiation of new therapy, or relapse (whichever is earliest)

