13.0 APPENDIX 2: Patient Evaluation Flow Sheet –Follow-up

	Monthly for 1 Year (± 10 Days)	Every 2-3 months for 1 year	Every 3-4 months for 1 year	Early Termination
Patient status report	X ¹			x
Hematology		x		x
Biochemistry		x		
Copper levels	only if abnormal ²			
Bone Marrow Aspiration/Biopsy			
x
 
For patients in CR, consider performing if peripheral blood counts fall below 1000/μL for ANC or 100,000/μL for platelets for >1 month with no obvious explanation for the drop or at any time there is suspicion of relapse; for patients in CRI perform if counts fall significantly below peak recovery. If the peripheral blood counts in a patient with a CRI recover to CR levels ($\geq 1000/\mu$L for ANC or $\geq 100,000/\mu$L for platelets), consider performing a bone marrow evaluation to confirm full CR. Following the first year of follow up, aspirations will be done as clinically indicated; record relapse information, including any bone marrow evaluations. Not required following the initiation of new therapy and or relapse.
	
Echocardiography or MUGA scan			
x
 
Perform every 3-4 months if last Treatment Phase LVEF was reduced >10% from baseline and is less than 50%. Continue assessments until LVEF returns to baseline or until 1 year from start of therapy.
	

¹ Survival followed until death

²>20% above upper limit of normal. To be performed monthly until return to within 20% of ULN, or until 1 year from the last dose, or the initiation of new therapy, or relapse (whichever is earlier).

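### The promised percentage with copper raised for more than 1 year does not fit a test schedule that ends at 1 year, relapse or new therapy

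*Combined protocol and SAP*

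**What the plan says.** Four places in the combined protocol and SAP bear on this.

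- **Section 9.4.1** sets the output: "the percentage of patients with persistent (>1 year) copper elevations will be reported". It does not say when the year begins, what level counts as elevated, or which patients form the denominator. It also asks for a clinical work-up of patients whose copper stays high.
- **Section 6.4** decides who is tested after treatment: "Perform monthly only if elevated copper (>20% above ULN) present at EOT". Testing ends when copper is no more than 20% over the upper limit of normal (ULN), "or until 1 year, or the initiation of new therapy, or relapse (whichever is earliest". The start of that year is not given. The follow-up phase as a whole runs "after completion of all therapy to continue for one year except for survival and relapse status".
- **Appendix 2** repeats these stops with a start date: "or until 1 year from the last dose, or the initiation of new therapy, or relapse (whichever is earlier". Its column for monthly assessments is headed "Monthly for 1 Year (± 10 Days".
- **Section 2.7** takes a different line: "Serum copper levels will be monitored until they return to baseline levels", with a margin of 20% either way. It mentions no limit at 1 year, relapse or new therapy.

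Section 10.0 has no analysis of copper and no rule for patients whose copper tests end early.

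**The concern.** The output is defined by what happens after 1 year, while both operative schedules finish at 1 year or sooner. If the schedules are followed as written, few patients can supply a test that could put them in the numerator, and those who can are a selected group.

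A percentage at or near zero would then reflect the schedule at least in part. Section 2.7 already expects no safety problem from copper, so such a figure could easily be taken as confirmation that copper clears. The undefined term also reaches beyond the results table, because section 9.4.1 ties the clinical work-up to persistent elevation.

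**Working it through.** The plan gives no figure to reproduce, so the check compares the wording of the output with the days on which tests are planned.

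**Inputs.** Copper testing stops 1 year after the last dose, with a monthly visit window of ±10 days (Appendix 2). First induction is dosed on Days 1, 3 and 5 (section 4.0). Second induction and consolidation are dosed on Days 1 and 3 (sections 4.5 and 4.6). There are at most two inductions (section 7.5), and "A maximum of 4 courses of consolidation will be administered" (section 4.6).

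**Assumptions on timing.** Second induction starts on Day 28, first consolidation starts 42 days after the start of the last induction, and consolidations start 28 to 56 days apart. The protocol allows variation around all of these.

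**Year counted from the last dose.** The final monthly visit falls on day 365 ± 10, that is days 355 to 375. Only a visit made late within its window gives a value beyond day 365.

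**Year counted from the first dose.** Let L be the days from first to last dose. The schedule then ends on day L + 365, and the final visit falls between L + 355 and L + 375.

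| Courses | L | End of schedule | Final visit |
|---|---|---|---|
| One induction | 4 | 369 | 359–379 |
| Two inductions | 27 + 2 = 29 | 394 | 384–404 |
| One induction, one consolidation | 42 + 2 = 44 | 409 | 399–419 |
| One induction, four consolidations 28 days apart | 42 + 3×28 + 2 = 128 | 493 | 483–503 |
| Two inductions, four consolidations 28 days apart | 27 + 42 + 3×28 + 2 = 155 | 520 | 510–530 |
| Two inductions, four consolidations 56 days apart | 27 + 42 + 3×56 + 2 = 239 | 604 | 594–614 |

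After a single induction the margin is 4 days, less than the 10-day window, so the final test may fall on either side of 1 year. With more than one course the final test does pass day 365, provided relapse or new therapy has not ended testing. Patients without a response after two inductions move to survival follow-up alone (section 4.5), so the two-induction row applies in practice to responders.

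The first-dose count also measures something different. With L = 155, day 366 is only 366 − 155 = 211 days after the last dose. With L = 239 it is 366 − 239 = 127 days. An elevation then says little about persistence for a year after treatment.

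**The rules side by side.**

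| | Section 2.7 | Section 6.4 | Appendix 2 |
|---|---|---|---|
| Reference level | Baseline ±20% | 20% over ULN | 20% over ULN |
| Time limit | None | 1 year, start not stated | 1 year from last dose |
| Stops at relapse or new therapy | No | Yes | Yes |

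Section 9.4.1 does not say which column it relies on.

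**The case against.** A reader might infer that an elevation beyond 1 year can never be observed, so that the result is 0% by construction. The documents do not support that. Section 9.4.1 fixes no start date; counting from the first dose moves the end of the schedule past day 365; the visit window allows a late final test; and section 2.7, taken alone, sets no cap. What stands is narrower: the operative schedules do not reliably provide the observation.

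A reader might also infer that patients whose testing ends early would be counted as resolved. No section says so. The denominator is simply undefined.

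Nor can the loss be sized from the 1-year survival figures in section 2.1 (22–35% with one or two risk factors, 8% with three or more). They come from a cohort aged 65 or older with a different list of risk factors, and follow-up copper tests apply only to patients elevated at end of treatment. Section 2.7 reports that every patient in the Phase I cohort shown had normal copper by day 42 after first induction. Most patients may therefore leave testing because copper has normalised, and a low percentage could be true.

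Finally, the wording in section 9.4.1 may be loose shorthand for still being elevated when the one-year schedule ends. That is a sensible reading, and data for it would exist. But it is not what the text says, and it still leaves patients stopped by relapse, new therapy or death unaccounted for. A low figure would be plausible on clinical grounds and also favoured by the schedule, and the planned report could not tell the two apart.

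**Conclusion.** The point holds as a mismatch between a stated safety output and the schedule meant to supply it. From the last dose, no planned test is reliably beyond 1 year. From the first dose, observation is clear only after more than one course without relapse or new therapy. The direction of the bias is towards zero. Its size cannot be worked out, because the documents do not give the number elevated at end of treatment or the rates at which testing would end early.

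The last-dose conclusion rests on Appendix 2 as written, and the first-dose figures rest on the assumed course spacing. Section 2.7 separately conflicts with section 6.4 and Appendix 2 on both threshold and stopping. The weight is small: the primary response analysis, DLT monitoring, sample size and error rates are unaffected.

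**What to change.** 1. In section 9.4.1, replace the percentage beyond 1 year with the number and percentage of patients still elevated at their last scheduled copper test, among those elevated at end of treatment. Give the time of that test from the last dose and the reason testing ended: normalised, 1 year reached, relapse, new therapy or death. State how many patients had no end-of-treatment copper value.
2. Optionally, add a cumulative incidence of copper return, with death, relapse and new therapy as competing events. With at most 80 patients in the trial, and fewer elevated at end of treatment, the descriptive table may be enough.
3. Reconcile sections 2.7, 6.4, 9.4.1 and Appendix 2 on the start date, the elevation threshold and the stop rule. Which rule should govern is for the sponsor and investigators; this review does not choose.

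Items 1 and 2 use tests already scheduled and cost a little extra descriptive analysis. Item 3 is a wording change, but depending on the rule chosen it could alter who is tested and for how long.

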10.0 Statistical Considerations(16, 17)

General Description:

This is a Phase II study of CPX-351 Liposome Injection in newly diagnosed AML patients with high risk of induction mortality. Two dose levels (50 units/m² and 75 units/m²) of CPX-351 will be studied initially. The primary objective is to evaluate treatment response. The efficacy outcome is CR or CRi within two induction cycles. A maximum of 30 patients will be equally randomized to the two dose levels. A Bayesian method by Thall et al (1995)

will be used for futility and toxicity monitoring. After 15 patients have been accrued to each dose level, an assessment of overall safety/dose limiting toxicities and efficacy will be made and one dose level will be chosen for further study. OR if both dose levels are safe and further dose escalation seems possible, one additional cohort with a dose of 100 units/m² will be open. A maximum of 15 patients will be enrolled in this arm and the same toxicity and futility monitor rules will be applied. After 2 or 3 dose levels have been studied, one dose levels will be chosen for further study. An expansion cohort of 10 patients will be treated at the dose level with a favorable response and/or toxicity profile for further evaluation for safety and efficacy. Consequently, the preferred dose level has 25 patients evaluable.

Additional 25 patients will be added to the arm with the dose of 100 units/m², the sample size for this arm will be up to 40, and the maximum number of patients for all three arms will be up to 80.

Multc Lean software version 2.1 developed in the Department of Biostatistics MDACC was used for the study design.

The study will monitor futility and toxicity, and the monitoring rules will be applied to each dose separately. If study in one of the two doses is stopped early due to futility or excessive toxicity, all the future patients will be enrolled in the open dose arm (i.e., without randomization). In the case the lower dose (50 units/m²) has been shown to be too toxic at an interim look (thus stop further patient enrollment) the higher dose (75 units/m²) will also stop accrual.

Futility monitoring:

Treatment success is defined as achievement of CR or CRi. We will accrue a maximum of 15 patients at each dose level and test the null hypothesis that the true response is at most 5% (meaning little or no activity) versus the alternative hypothesis that the true response is 30% or greater, independently in each treatment arm. Assuming that the success rate is binomially distributed, this design with 15 patients in each arm has 87% power and a one-sided type I error rate of 0.05 using an exact test.

To monitor futility, the study in one dose level will be stopped early if the data in that dose level suggest that:

$$\Pr(\theta_E < 0.25 + \theta_s | \text{data}) > 0.95$$

That is, if at any time during the study we determine that there is a greater than 95% chance that the response rate is less likely to improve by 25% than the null hypothesis in one dose level, we will terminate the enrollment in that dose. Here θ_E represents the response rate for experimental drug in this study and θ_s represents the response rate for the standard practice (null hypothesis). We assume that θ_s has a distribution of beta (10, 190) to reflect the information on 200 patients for the historical data, which has a mean response rate of 0.05 and a variance of 0.0002. We also assume that θ_E has a non-informative flat prior beta(0.1, 1.9) with mean of 0.05 and variance of 0.0158.

The futility stopping boundaries for the overall response based on these assumptions and monitoring condition is shown in table 7. For example, accrual will be stopped in one dose if there is no response observed in the first 5 patients treated in that dose.

The toxicity monitoring/efficacy summary will be submitted to the IND Office Medical Monitor ([name]) for every 5 subjects treated in each Arm (per Table 7, 8, 11 & 12).

Table 7: Stopping boundaries for futility monitoring for the initial cohort of each dose (n=15)

# Patients (in complete cohorts of 5) (inclusive)	Stop the enrollment in one dose if there are this many responses total in that dose:
